5.1.1.1.4 Estimands

Estimands for Global Part 1 primary, key secondary, and secondary endpoints are provided below:

Table 5-3 Estimand Language

Endpoint: Global Part 1	Estimand Language
Primary	
 Population: All randomized subjects with NASH CRN fibrosis stage 2 or 3 who also met inclusion and exclusion criteria for the study. The analysis population is the modified ITT population. Variable/Endpoint: Improvement in fibrosis by at least 1 stage (NASH CRN system) AND no worsening of steatohepatitis (no worsening of lobular inflammation or hepatocellular ballooning grade 2005) on liver histology at Month 12 relative to Screening biopsy Intercurrent Event: Hypothetically envisage that those who withdraw from the study prior to the liver biopsy at Month 12 or those who do not have readable liver biopsies at the Month 12 visit assessment will be considered as non-responders (those who do not improve in fibrosis stage). Population-level Summary: Difference in responder rates from screening biopsy for fibrosis stage improvement (with no worsening of steatohepatitis) at Month 12 between the CVC group versus the placebo group using the Cochran-Mantel-Haenszel (CMH) test, stratified by NASH CRN fibrosis stage (2 vs 3) and T2DM at baseline (presence vs absence)
Key Secondary	
 Population: All randomized subjects with NASH CRN fibrosis stage 2 or 3 who also met inclusion and exclusion criteria for the study. The analysis population is the modified ITT population. Variable/Endpoint: Improvement in fibrosis by at least 2 stages (NASH CRN system) AND no worsening of steatohepatitis (no worsening of lobular inflammation or hepatocellular ballooning grade 2005) on liver histology at Month 12 relative to Screening biopsy Intercurrent Event: Hypothetically envisage that those who withdraw from the study prior to the liver biopsy at Month 12 or those who do not have readable liver biopsies at the Month 12 visit assessment will be considered as non-responders (those who do not improve in fibrosis stage). Population-level Summary: Difference in responder rates from screening biopsy for fibrosis stage improvement (with no worsening of steatohepatitis) at Month 12 between the CVC group versus the placebo group using the Cochran-Mantel-Haenszel (CMH) test, stratified by NASH CRN fibrosis stage (2 vs 3) and T2DM at baseline (presence vs absence)

Endpoint: Global Part 1	Estimand Language
Secondary	
 • Population: All randomized subjects with NASH CRN fibrosis stage 2 or 3 who also met inclusion and exclusion criteria for the study. The analysis population is the modified ITT population. • Variable/Endpoint: Improvement in fibrosis by at least 1 stage (NASH CRN system), regardless of effect on steatohepatitis, at Month 12 relative to Screening biopsy • Intercurrent Event: Hypothetically envisage that those who withdraw from the study prior to the liver biopsy at Month 12 or those who do not have readable liver biopsies at the Month 12 visit assessment will be considered as non-responders (those who do not improve in fibrosis stage). • Population-level Summary: Difference in responder rates from screening biopsy for fibrosis stage improvement at Month 12 between the CVC group versus the placebo group using the Cochran-Mantel-Haenszel (CMH) test, stratified by NASH CRN fibrosis stage (2 vs 3) and T2DM at baseline (presence vs absence) 
The other secondary endpoint (same as above secondary endpoint but with improvement by “at least 2 stages”) will be analyzed similarly.

The EU-specific estimands will be as follows:

- EU primary estimand: same as the Global Part 1 key secondary estimand
- EU key secondary estimand: none
- EU secondary estimands: same as the Global Part 1 secondary estimands

5.1.1.1.5 Missing Data

General missing data handling conventions are specified for methodologies in Section 5.1.1.1.3 and summarized as follows:

Table 5-4 Missing Data Handling by Endpoint Type

Parameter type	Timing	Missing Data Handling
Responder (Part 1: primary endpoint at Month 12)	Screening, Month 12	
 • All subjects in mITT analysis set included. Subjects with missing baseline biopsy data should not be randomized in the study. • Any available adequate liver biopsy after baseline will be used as the biopsy for the target visit (ie., Month 12), no matter when it was obtained relative to the first dose of study drug. • Subjects with multiple liver biopsies will have the evaluable biopsy closest to the target visit included in the analysis. • Subjects who do not have an evaluable liver biopsy at both Screening and the target visit will be included in the analyses as nonresponders. • Summaries of subjects who do and who do not have evaluable liver biopsies at the target visit will be provided to assess whether demographics, baseline data or safety data are predictive of missingness.

Parameter type	Timing	Missing Data Handling
		
 Subjects who do not have an evaluable biopsy at the target visit will be those with no post baseline liver biopsy or those with a biopsy reading of non-evaluable from the central reader. Sensitivity analyses for the primary efficacy endpoint will be performed, accounting for both missing at random and missing not at random scenarios.
Responder (Part 2: secondary endpoint at Month 60)	Screening, Month 60	
 Same as above for target visit, Month 60
Time-to-event (Part 2: primary endpoint)	Treatment Period	
 All subjects in mITT analysis set included. Any available adequate liver biopsy after baseline will be used for assessment of components of the clinical endpoint that require a biopsy, no matter when obtained. Subjects with multiple liver biopsies will be included as an event if any (one or more) biopsy meets the definition of the primary endpoint, as determined by the adjudication committee. Subjects who do not have an evaluable liver biopsy at both Screening and post-baseline will be included in the analyses as having an event only if they meet a component that does not require a biopsy; otherwise they will be included as not having an event and censored at the last visit. Subjects with partial follow-up data will be included as an event if they meet the criteria for any component of the primary efficacy endpoint, and as a nonevent if they do not meet the criteria for any component. A sensitivity analysis assuming data are missing not at random will be reported. An additional sensitivity analysis imputing an event at the time of censoring will also be reported, although it is anticipated that this analysis will not be informative unless many subjects discontinue due to unobserved NASH progression, which cannot be known.
CFB ANCOVA	Months 6 and 12 in Part 1, and Month 12 and annually thereafter in Part 2 (Month 6 in Part 2 for some endpoints)	
 If missing covariates (including baseline if applicable) 
 Subject excluded Observed data for mean absolute change and relative change from baseline to the times specified in the endpoints will be analyzed. There is no imputation for missing data.
Multiple imputation (Part 1: primary efficacy endpoint)	Month 12 MAR and MNAR	
A sensitivity analysis for the primary efficacy analysis in Part 1 will use multiple imputation to investigate the impact of missing data under a Missing At Random (MAR) assumption. For this analysis, the Month 12 biopsy results will be imputed for the subjects who do not have an evaluable biopsy after baseline. The imputation model will be defined before Part 1 unblinding to avoid the addition bias.
 
The multiple imputation model will use the MI procedure in SAS, using code such as the following:
 <pre>proc mi data=<inputdsn> seed=1305417 nimpute=100 out=<outputdsn>; class outcome trt; var trt <explanatory> outcome;</pre>

Parameter type	Timing	Missing Data Handling
		
monotone logistic (outcome=trt <explanatory>); run;
 
The variables in the imputation model (“explanatory” in the pseudocode above) will be defined before the database is locked for Part 1 and documented in an amendment to the SAP. Explanatory variables are expected to include baseline values of age, weight change from baseline to Month 12, BMI, sex, race, site, and other baseline values, stratification factors of fibrosis stage at baseline [2 vs 3] and T2DM at baseline [presence vs. absence], and post-randomization variables that correlate with the Part 1 primary endpoint among subjects with complete data based on review before unblinding.
 
Data from each imputation will be analyzed by CMH using code such as the following:
 <pre>PROC FREQ DATA=<outputdsn>; TABLES stratification * trt * outcome / CMH; ODS OUTPUT CMH=cmh; BY _Imputation_; RUN;</pre> 
Data from the multiple imputations will be combined with Rubin’s rule after application of the Wilson-Hilferty transformation. Each imputation will be analyzed using the primary analysis method (CMH) and the results combined with the MIANALYZE procedure in SAS. The p-value for treatment will be reported.
 
SAS code such as the following will accomplish this analysis:
 <pre>** Apply W-H transformation; DATA cmh_wh; SET cmh(WHERE=(AltHypothesis="General Association")); cmh_value_wh=((VALUE/DF)**(1/3) - (1-2/(9*DF)))/ SQRT(2/(9*DF)); cmh_sterr_wh = 1.0; RUN;</pre> <pre>*** Combine results; PROC MIANALYZE DATA=cmh_wh; ODS OUTPUT PARAMETERESTIMATES=mian_cmh_wh; MODELEFFECTS cmh_value_wh; STDERR cmh_sterr_wh; RUN;</pre> <pre>*** Compute one-sided p-value; DATA mian_cmh_wh_p; SET mian_cmh_wh; IF tValue > 0 THEN Probt_upper = Probt/2; ELSE Probt_upper = 1-Probt/2; RUN;</pre> 
A sensitivity analysis for the primary efficacy analysis in Part 1 will use pattern-mixture model (PMM) with a control-based pattern imputation (or jump to reference) to investigate the impact of missing data under a Missing Not At Random (MNAR) assumption. First, we will impute missing data at time-point Month 12. In order to do it using

Parameter type	Timing	Missing Data Handling
		
the control-based imputation method, we will separate our data into two datasets: DATAIN_MONO_IMP12, containing all placebo subjects and those subjects from the CVC arm that have values at time-point Month 12 missing; and DATAIN_MONO_REST12, containing the rest of the subjects from the CVC arm (those with non-missing SCORE_12).
 
We will now call PROC MI to impute missing data at time-point Month 12 based on the model estimated exclusively from placebo subjects with non-missing values at time-point Month 12.
 <pre>proc mi data=DATAIN_MONO_IMP12 seed=234 nimpute=100 out= DATAIN_REG_IMP12 class outcome ; var <explanatory> outcome; monotone logistic (outcome= <explanatory>); run;</pre> 
The following data step assembles back a dataset containing all subjects.
 <pre>data DATAIN_IMP1; set DATAIN_MONO_REST1 DATAIN_REG_IMP1; run;</pre> 
Data from each imputation will be analyzed using CMH and results will be combined using following codes.
 <pre>PROC FREQ DATA=DATAIN_IMP1; TABLES stratification * trt * outcome / CMH; ODS OUTPUT CMH=cmh2; BY _Imputation_; RUN;</pre> <pre>DATA cmh_wh2; SET cmh2(WHERE=(AltHypothesis="General Association")); cmh_value_wh=((VALUE/DF)**(1/3) - (1-2/(9*DF)))/ SQRT(2/ (9*DF)); cmh_sterr_wh = 1.0; RUN;</pre> <pre>*** Combine results; PROC MIANALYZE DATA=cmh_wh2; ODS OUTPUT PARAMETERESTIMATES=mian_cmh_wh2; MODELEFFECTS cmh_value_wh; STDERR cmh_sterr_wh; RUN;</pre> <pre>*** Compute one-sided p-value; DATA mian_cmh_wh_p; SET mian_cmh_wh2; IF tValue > 0 THEN Probt_upper = Probt/2; ELSE Probt_upper = 1-Probt/2; RUN;</pre>

Parameter type	Timing	Missing Data Handling

Multiple imputation (Part 2: primary efficacy endpoint)
	
Treatment Period
	
Informative Censoring Imputation Model:⁶
 
Let k index the censoring times before t^*. (Note: $t^* \approx 96$ months for subjects randomized in Part 1 and 84 months newly randomized subjects in Part 2.)
 
Let $t_{k,0}$ denote the latest failure time prior to c_k (or equal to it) when $t_1 \leq c_k$.
 
Let $t_{k,j}$ denote the jth failure time after c_k, $j = 1, 2, \dots, J_k$, when $c_k < t_M$. Note that the possible values of J_k range from 1 to M, depending on the position of c_k with respect to the order of the t_m's ($m = 1, 2, \dots, M$): J_k equals M if $c_k < t_1$, and J_k equals 1 if $t_{M-1} = c_k < t_M$. From the observed data, we obtain the Kaplan–Meier estimates $\hat{S}(t)$ for the survival distribution for the event times, and it has support on the observed event times (t_1, t_2, \dots, t_M).
 
The estimate for the conditional cumulative incidence function for a subject with early discontinuation at c_k to have the event by the time t in $[t_{k,j} < t < t_{k,j+1}]$, for $j = 1, 2, 3, \dots, J_k$ with $t_{k,J_k+1} = t^*$ can be obtained as follows.
 $\hat{F}_{j,k}(\theta) = 1 - \frac{\hat{S}(t_{k,j+1})^\theta}{\hat{S}(c_k)^\theta}$ 
The estimate for the conditional probability for a subject with early discontinuation at c_k to have the event by the time t in $[c_k < t < t^*]$, can be obtained as follows.
 $\hat{f}_{j,k}(\theta) = \frac{\hat{S}(c_k)^\theta - \hat{S}(t^*)^\theta}{\hat{S}(c_k)^\theta}$ 
Under this formulation, $\theta > 1$ (or < 1) implies a higher (or lower) hazard after c_k for patients with premature discontinuation at c_k than for patients with continued follow-up after c_k. The test treatment group would usually have $\theta_{\text{active}} > \theta_{\text{placebo}}$ specified, and with $\theta_{\text{placebo}} = 1$, $\theta = (\theta_{\text{active}} / \theta_{\text{placebo}}) = \theta_{\text{active}}$ becomes a single parameter for calibrating sensitivity analyses. The value of θ_{active} will be finalized before database lock.
 
*** To obtain the survival function estimates $\hat{S}(t_{k,j+1})$ and $\hat{S}(c_k)$ to generate $\hat{f}_{j,k}(\theta)$ and $\hat{F}_{j,k}(\theta)$:
 <pre>proc lifetest data=xxx OUTSURV=SURVEST; time AVAL*CNSR(1); strata ARMCD / test=logrank; SURVIVAL CONFTYPE=LINEAR; run;</pre> 
In SURVEST datasets, SURVIVAL column is what we need to obtain the survival function estimates. Please note that $\hat{F}_{j,k}(\theta)$ is from 0 to 1. The multiple imputation scheme is as follows:
 
 1. Generate a random number p from the uniform distribution between 0 and 1, and for computational convenience, use linear interpolation to impute failure times.

Parameter type	Timing	Missing Data Handling
		
Use UNIFORM function in SAS to generate a pseudorandom number p from the uniform distribution on $[0, 1]$ for the following scenario.
 
 2. Suppose a subject has early discontinuation at time c_k, perform the following failure time imputation: 
 a. If $0 \leq p \leq \hat{F}_{k,0}(\theta)$, then impute the failure time $t_k^{(l)}$ between c_k and $t_{k,1}$ as $c_k + (t_{k,1} - c_k) \frac{p}{\hat{F}_{k,0}(\theta)}$, where l indicates the lth imputation set. b. If $\hat{F}_{k,j}(\theta) \leq p \leq \hat{F}_{k,j+1}(\theta)$, for $j = 0, 1, 2, 3, \dots, (J_k - 1)$, then impute failure time $t_k^{(l)}$ between $t_{k,j+1}$ and $t_{k,j+2}$ as $\left(t_{k,j+1} + (t_{k,j+2} - t_{k,j+1}) * \frac{p - \hat{F}_{k,j}(\theta)}{\hat{F}_{k,j+1}(\theta) - \hat{F}_{k,j}(\theta)} \right)$, where $t_{k,J_k+1} = t^*$. c. If $p > \hat{F}_{k,J_k}(\theta)$, then manage the patient as having no event by the end of follow-up time t^*. 3. Suppose a patient has premature discontinuation between t_M and t^*, so that $(t_M < c_k < t^*)$: 
 a. If $p \leq \hat{f}_{j,k}(\theta)$, then impute failure time $t_k^{(l)}$ between c_k and t^* as $c_k + (t^* - c_k) \frac{p}{\hat{f}_{k,0}(\theta)}$; b. Otherwise, manage the patient as having no event by the end of follow-up time t^*. 
The imputation is performed separately for the patients with premature discontinuation in each treatment group.
 
The above imputation procedure is repeated to form L imputed data sets.
 
*** Combining Chi-square distributed statistics after multiple imputation: After multiple imputation, it is possible to combine the test results from all available tests in PROC LIFETEST such as log-rank test. Each of these tests is based on a chi-square distributed statistic that can be normalized using a Wilson-Hilferty transformation. If X^2 is chi-square distributed with d degrees of freedom, then
 $W = \sqrt[3]{\frac{X^2}{d}} \approx N\left(1 - \frac{2}{9d}, \frac{2}{9d}\right), \text{ or}$ $\frac{\sqrt[3]{X^2/d} - \left(1 - \frac{2}{9d}\right)}{\sqrt{\frac{2}{9d}}} \approx N(0,1)$ 
Test statistics and their corresponding degrees of freedom can be found in the ODS output dataset HomTests produced by PROC LIFETEST when using the STRATA statement with TEST option. These test

Parameter type	Timing	Missing Data Handling
		
statistics obtained from each imputed dataset can be normalized using the above formula and the normalized values can let be input for PROC MIANALYZE in order to obtain combined results for these chi-square based tests.
 <pre> DATA _tmc_tests1; set _tmc_tests; *** ChiSq is a chi-square distributed statistic (e.g., logrank) and DF is its corresponding degrees of freedom as produced by PROC LIFETEST ***; ChiSq_wh=((ChiSq/DF)**(1/3) - (1-2/(9*DF)))/SQRT(2/(9*DF)); ChiSq_stderr_wh = 1.0; run; proc sort data=_tmc_tests1; BY _Imputation_; run; proc MIANALYZE data=_tmc_tests1; modeleffects ChiSq_wh; stderr ChiSq_stderr_wh; ods output parameterestimates=resprefix._tests; run; *** Combining results of Cox regression and exponentiation of the combined log-hazard ratios: Cox regression model parameter estimates from PROC PHREG represent log hazard ratios. They are normally distributed and do not need any further transformation to be combined with Rubin's rules using PROC MIANALYZE. However, the end results need to be exponentiated to obtain the numerical values of the hazard ratios and associated confidence intervals. proc phreg data=_tmc_1; by _Imputation_; class trtvar <classvars>; model timevar * censvar(censval) = trtvar covars / risklimits ties=efron rl; ods output ParameterEstimates=_es; run; /* Combine model coefficients. */ proc sort data=_es; by Parameter ClassVal0 _Imputation_; run; proc MIANALYZE data=_es; by Parameter ClassVal0; modeleffects Estimate; stderr stderr; ods output ParameterEstimates = _es_mianal; run; /*Exponentiate in order to obtain hazard ratio estimates and confidence intervals */ data resprefix. hr; </pre>

Parameter type	Timing	Missing Data Handling
		<pre>set_es_mianal; Log_HR_comb=Estimate; HR_comb=exp(Estimate); HR_LCL_comb=exp(LCLMean); HR_UCL_comb=exp(UCLMean); keep Parameter ClassVal0 Log_HR_comb HR_comb HR_LCL_comb HR_UCL_comb Probt; rename Probt=HR_pval_comb; run;</pre>

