### **11.2. Assessments of Efficacy**

In Part 1, subjects meeting all eligibility criteria and with suspicion of significant liver fibrosis (through clinical, hepatic fibrosis indices, and/or liver stiffness assessment) will have a liver biopsy read by an independent central pathologist during the Screening period. In randomized subjects, a second post-treatment liver biopsy will be collected within  $\pm 2$  weeks of the Month 12 visit.

In Part 2, newly enrolled subjects will undergo a liver biopsy at Screening for assessment of eligibility and a second post-treatment liver biopsy will be collected within  $\pm 2$  weeks of the

Month 12 visit. All subjects (newly randomized subjects with a liver biopsy diagnosis of NASH and Stage 3 liver fibrosis (by NASH CRN system) and those who continue from Part 1) will undergo a liver biopsy at Month 60 (within  $\pm$  2 weeks) after first dose of study drug.

At the end of study, if a subject has received study drug for at least 6 months and has not had the Month 60 biopsy, then a biopsy should be taken within 30 days of the end of study, if feasible.

Liver biopsies will be performed per standard of care (eg, taking into account the subject's health status, coagulation profile, and use of concomitant medications). Subjects who discontinue study drug are encouraged to continue with all other evaluations as scheduled in this protocol, including biopsies and other invasive procedures at the scheduled visits. If a subject discontinues study participation early and has received study drug for at least 6 months in Part 1 or Part 2, then a biopsy should be taken within 30 days of discontinuation, if feasible. All liver biopsies will be evaluated by an independent central pathologist; whenever possible, the same pathologist will evaluate all biopsies from an individual subject. The independent central pathologists will be blinded to individual treatment assignment.

Liver biopsy at Screening and Months 12 and 60 will be used to determine improvement in histologic fibrosis stage (NASH CRN – the system used to assess the primary efficacy endpoint – and Ishak systems).

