Month 60 per protocol (PP2)	
All subjects randomly assigned to a treatment group who have an evaluable biopsy at Screening, have no significant protocol deviations that potentially influence the primary efficacy assessment, and either:
 
 • Have an adjudicated event that is a component of the primary composite endpoint within 24 months after randomization 
OR
 
 • Have at least 24 months of follow-up for clinical events AND one of the following: 
 • Have an adjudicated event that is a component of the primary composite endpoint within 6 months of last intake of study drug 
OR
 
 • Have a biopsy at least 24 months after randomization and within 6 months of last intake of study drug. 
This will be a supportive analysis set for selected efficacy analyses of Part 2.
	Randomized assignment
Safety	
All subjects who received ≥ 1 dose of study drug will be included in the safety analysis set. Subjects will be included in the treatment group according to actual treatment received, even if they receive a different treatment than that to which they are randomly assigned. Subjects who inadvertently receive both treatments will be included with the CVC group.
 
This will be the primary analysis set for the safety analyses.
	Actual received ¹
Pharmacokinetic	All subjects who are randomized and receive at least one dose of study drug and have at least one post-dose PK sample will be included in the PK analysis set.	Randomized assignment

¹ Subjects will be summarized according to the study treatment received.

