6.2 Analysis Visit Windows

6.2.1 Efficacy

The analysis visit windows for efficacy endpoints, including liver biopsy, are defined as follows:

Table 6-2 Efficacy Analysis Visit Definitions

Analysis Phase	Analysis Visit (Derived)	Study Visit (eCRF)	Window
Part 1 & Part 2			
Pretreatment	Baseline	Day 1	Treatment Day ≤ 1 , pre-randomization in Part Y
Treatment	Month 12	Day 360	Treatment Day [316, 405], post-randomization in Part 2 Note: For the primary efficacy analysis in Part 1 using the mITT analysis set, any available liver biopsy after randomization will be used for the Month 12 biopsy, no matter when it was obtained relative to the first dose of study drug. Subjects with multiple liver biopsies will have the evaluable biopsy closest to the Month 12 visit included in the analysis.
	Month 60	Day 1800	Treatment Day [1756, 1845], post-dose in Part 2
	End of study	Final or termination visit	Last non-missing assessment during the Treatment Period in Part Y / between Treatment Day 1 in Part Y, post-dose, and Off-treatment Day 1, inclusive, where Y=1, 2.

The following general conventions for repeated or unscheduled assessments will apply unless otherwise specified:

- For scheduled and unscheduled assessments, if more than one assessment is measured within the same visit window, then the record with the latest visit date (from baseline) will be used for that visit window.
- All assessments will be included in respective listings.

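### SAP Table 5-4 lets a Month 12 biopsy stand in for a missing Month 60 biopsy, contrary to the Month 60 window in Table 6-2

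*SAP*

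**What the plan says.** The Month 60 row of Table 5-4 (SAP 5.1.1.1.5) reads "Same as above for target visit, Month 60". Three bullets come with it from the Month 12 row:

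- Biopsy choice: "Any available adequate liver biopsy after baseline will be used as the biopsy for the target visit (ie., Month 12), no matter when" it was taken.
- Several biopsies: the evaluable one nearest the target visit is used, with no maximum distance.
- Who is missing: "Subjects who do not have an evaluable biopsy at the target visit will be those with no post baseline liver biopsy", or those whose central reading is non-evaluable. Missing subjects are nonresponders.

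Table 6-2 (SAP 6.2.1) states that its windows cover liver biopsy. It sets Month 60 at "Treatment Day [1756, 1845], post-dose in Part 2". Its only waiver of a window is a note in the Month 12 row: "For the primary efficacy analysis in Part 1 using the mITT analysis set, any available liver biopsy after randomization will be used".

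Protocol 11.2 provides some late biopsies. One is requested at end of study "if a subject has received study drug for at least 6 months and has not had the Month 60 biopsy". For a subject who leaves the study early after at least 6 months on drug, "then a biopsy should be taken within 30 days of discontinuation, if feasible".

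Table 5-14 reports the Part 2 secondary endpoints on the mITT and PP2 sets.

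**The concern.** The Month 60 endpoints ask whether fibrosis is better at five years than at Screening. Under Table 5-4 as written, some subjects answer that question with tissue taken at about one year. If CVC works at Month 12, their results bring the Month 12 difference into the Month 60 comparison, and a benefit that has faded can look durable.

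Later clinical failure makes this worse. Subjects with an adjudicated liver outcome leave the study (Protocol 7.1; SAP 4.1.1). A Month 12 responder who then dies, or develops ascites, without a further biopsy would count as a Month 60 success. Table 5-3 defines estimands for Part 1 only, so no Month 60 event rule prevents this.

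Three groups are not affected:

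- subjects with a later evaluable discontinuation or end-of-study biopsy, which is nearer to Month 60 than the Month 12 biopsy;
- subjects with biopsy-proven cirrhosis, who are nonresponders on that biopsy;
- subjects with no post-baseline biopsy, who are already nonresponders.

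**Working it through.** **The texts side by side.** Take a subject with an evaluable Month 12 biopsy and none afterwards. Table 5-4 has an available post-baseline biopsy, which is also the nearest evaluable one, and the subject falls outside the definition of missing. The Month 12 result is used. Table 6-2 finds no biopsy between Day 1756 and Day 1845, and its waiver does not reach Month 60, so there is no Month 60 result. The nominal Month 12 biopsy is at Day 360, which is 1756 − 360 = 1396 days before the window opens.

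**The plan's own figures.** The documents give no power for the Month 60 endpoints. The Month 12 rates used below are the planning rates in SAP 5.1.2, so I first reproduced the power quoted with them. The formula is Φ(|p1 − p2|/SE − z), with unpooled SE, 800 vs 400 subjects, two-sided alpha 0.0012 and z = 3.239.

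- 1-stage, 25% vs 15%: SE = √(0.15×0.85/400 + 0.25×0.75/800) = 0.02352, and 0.10/0.02352 = 4.252. Power is Φ(1.013) = 84.4%, against 84% stated.
- 2-stage, 8.6% vs 2.2%: SE = 0.01233, and 0.064/0.01233 = 5.190. Power is 97.4%, against 97% stated.

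**Carry-over model.** Inputs:

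- N = 1334 CVC and 666 placebo (SAP 4.1.2).
- p12 = Month 12 response rate by arm, as above.
- b = Month 60 rate, assumed equal in both arms so that the true difference is zero. Range 15-25% for 1-stage and 2.2-8.6% for 2-stage.
- m = share of each arm scored on Month 12, assumed equal in both arms.

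Arm rate = (1 − m)×b + m×p12. The b terms cancel, so the false difference is m×(p12 CVC − p12 placebo). The chance of p<0.05 comes from a two-sided pooled z test.

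Example with m = 0.20 and b = 0.20: CVC = 0.8×0.20 + 0.2×0.25 = 0.21; placebo = 0.8×0.20 + 0.2×0.15 = 0.19; difference 2 points. The null SE is 0.0191 and the alternative SE is 0.0189. The chance of rejection is Φ((0.02 − 1.96×0.0191)/0.0189) plus a lower tail of 0.001, or 0.179.

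| m | 1-stage difference (points) | chance of p<0.05 | 2-stage difference (points) | chance of p<0.05 |
|---|---|---|---|---|
| 5% | 0.5 | 0.056-0.059 | 0.32 | 0.055-0.067 |
| 10% | 1.0 | 0.077-0.087 | 0.64 | 0.075-0.124 |
| 20% | 2.0 | 0.163-0.203 | 1.28 | 0.160-0.337 |

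A simulation of 200,000 runs gave 0.056-0.058, 0.077-0.087 and 0.162-0.203 for the 1-stage endpoint. If the same subjects are scored as nonresponders, both arms have rate (1 − m)×b, the difference is zero and the chance is 5% at every m.

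**The case against.** **The SAP may not intend carry-forward.** Table 6-2 points the other way. One bullet in Table 5-4 makes subjects without an evaluable target-visit biopsy nonresponders. The protocol states the any-biopsy rule only for the Part 1 primary analysis and the Part 2 time-to-event endpoint. This stands as far as intent goes: the fault is an unresolved conflict between two SAP rules. But a later bullet in the same cell defines the missing group narrowly, and Protocol 12.1.4 says data are used without regard to visit windows, which makes carry-forward more likely to be programmed. One case is unclear even within Table 5-4: a subject with an evaluable Month 12 biopsy and a non-evaluable Month 60 reading.

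**The 20% row may be too high.** It equals the plan's whole dropout allowance (SAP 5.1.2). With constant dropout over five years, four fifths of 20% leave after Month 12, and 85% of those have a Month 12 biopsy: 0.20 × 0.8 × 0.85 = 13.6%. At 14% the 1-stage chance is 10-12%, before subtracting subjects with a discontinuation biopsy. Deaths, non-biopsy events and refused Month 60 biopsies add to that share. This is a fair caution on size.

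**The carried-forward subjects may not have the trial-wide Month 12 rates.** That is true, and it works in both directions. Those who later die or decompensate may have responded less. On the other hand, 25% and 15% count missing biopsies as nonresponse, whereas everyone carried forward has an evaluable biopsy. Dividing both rates by 0.85 gives 21-26% at m = 20%.

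**The problem would be partly visible.** Month 60 biopsy disposition is tabulated (SAP 5.1.1.2.2), and PP2 results are reported. The disposition table shows how many biopsies are missing but does not correct the estimate. PP2 is only a partial check, because one way into it is to "Have an adjudicated event that is a component of the primary composite endpoint within 24 months after randomization", and that route needs no late biopsy.

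**Conclusion.** The concern holds. Followed literally, Table 5-4 scores subjects who have only a Month 12 biopsy as Month 60 results. Table 6-2 contradicts this, and neither document says which governs.

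The false difference is 1 point per 10% of subjects carried forward for the 1-stage endpoint and 0.64 points for the 2-stage endpoint. With no true Month 60 difference, the chance of a nominal p<0.05 at 5%, 10% and 20% carried forward is about 6%, 8-9% and 16-20% (1-stage), and about 6-7%, 7-12% and 16-34% (2-stage), instead of 5%. These figures assume the planning Month 12 rates, equal carried-forward shares by arm and a common Month 60 rate. The share itself is not given in the documents.

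The endpoints are secondary and outside the alpha scheme, so neither primary test is affected. What is at risk is any claim of durable histological benefit. The SAP should be corrected before the Part 2 analysis.

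**What to change.** Replace the Month 60 row of Table 5-4 with a full rule, and align Table 6-2 with it:

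- A Month 12 biopsy never substitutes for Month 60.
- An evaluable biopsy in the Month 60 window is used.
- State whether discontinuation or end-of-study biopsies outside the window qualify. An earliest allowable day would be one way to keep late ones and exclude Month 12.
- Subjects without a qualifying biopsy are nonresponders, including those who died or left after an adjudicated event before having one. This is the plan's existing nonresponder convention (SAP Table 5-2).
- Say how a non-evaluable Month 60 reading is scored when an evaluable Month 12 biopsy exists.
- Choose between the nearest biopsy (Table 5-4) and the latest record in the window (SAP 6.2.1).
- Note that the rule is a specified exception to the general statement on visit windows in Protocol 12.1.4.

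The any-biopsy version can be kept as a sensitivity analysis. The cost is SAP wording and programming, with no new visits or data. Month 60 response rates will be somewhat lower because more subjects count as nonresponders.
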